7.12 End of trial

The end of the active study period is defined as the last Day 85 visit of the last subject participating in the trial. The end of the trial includes the late safety follow up period and is defined as the last Day 225 visit for the last subject participating in the trial. If the trial is terminated early, the trial ends when the Sponsor notifies the Investigator in writing that the trial has finished, or when the last subject attends the Day 255 visit, whichever is later. The Sponsor will notify the relevant competent authorities (CAs) and main Ethics Committees (ECs) of the end of a clinical trial within 90 days of its completion or 15 days if the trial is terminated early. A supplementary follow-up notification will be submitted to the relevant CAs and ECs after the last Day 225 visit.

8 TRIAL MEDICATION

8.1 Name and description of investigational medicinal product(s)

Vaccine FP-02.2

Vaccine FP-02.2 is a lyophilised product containing 0.6mg of nine different synthetic peptides (designated P877, P151, P113, P856(K), P753(K), P376, P797(K), P277(K) and P1266(K)), each covalently linked to a single fluorocarbon moiety on the N-terminus under a controlled process and 30mg Mannitol (EP grade). The nine peptides are 32 to 40 amino acids in length and correspond to conserved regions of Hepatitis B viral proteins. The fluorocarbon conjugated peptides, called fluoropeptides (the active Drug Substances), are designed to enhance the delivery of the antigens to the human immune system and induce therapeutic T cell responses against infection.

Vaccine FP-02.2 is a white to off-white powder presented in a 2mL clear glass vial sealed with a metal crimp. The vaccine is intended to be reconstituted with 600µl of 28mM L-histidine (EP grade) and 600µl sterile NaCl 0.9% in a total 1200µl to achieve a sterile, isotonic, neutral pH, clear to slightly translucent solution with no visible particles which will be injected intramuscularly. 1mL of the reconstituted Vaccine FP-02.2 will administer a 500µg/peptide dose. The reconstituted Vaccine FP-02.2 can be diluted with placebo component (see below) in order to administer 150µg/peptide dose in 1mL. Where applicable, Vaccine FP-02.2 can be prepared with IC31® to produce either a 500µg/peptide or 150µg/peptide dose both containing IC31® at a strength of 500nmol/mL KLK and 20nmol/mL ODN1a. Full preparation instructions and details of shelf life will be described in a separate pharmacy manual.

Placebo

The Placebo is comprised of placebo component (50mg/mL mannitol (EP grade) in 28mM L-histidine (EP grade)) diluted 1:1 in sterile NaCl 0.9%.

Placebo component is stored in 2mL glass vials containing 1.225mL of placebo component which, after thawing, is diluted 1:1 with sterile NaCl 0.9% to achieve an isotonic, neutral pH, clear and colourless solution, free from particulate matter which will be injected intramuscularly. Full preparation instructions and details of shelf life will be detailed in a separate pharmacy manual.

IC31®

IC31® is a two-component adjuvant composed of the synthetic peptide KLK and the synthetic oligodeoxynucleotide ODN1a. IC31® is packaged in 2mL clear glass vials and contains 1mL of a sterile turbid suspension, neutral pH at a strength of 1000nmol/mL KLK and 40nmol/mL ODN1a in 5mM phosphate and sterile NaCl 0.9%. IC31® is prepared by diluting 1:1 with placebo component. Full preparation instructions and details of shelf life will be detailed in a separate pharmacy manual.

8.2 Legal status of the drug

The trial is being carried out under a Clinical Trial Authorisation (CTA). Vaccine FP-02.2 and IC31® are therefore only to be used by the named Investigators, for the patients specified in this protocol, and within the trial.

8.3 Summary of Product Characteristics (SmPC)

Vaccine FP-02.2 and IC31® are not approved and there is no SmPC for the IMPs. Details of Vaccine FP-02.2 and IC31® can be found in the latest version of the IB.

8.4 Drug storage and supply

The Sponsor will supply Vaccine FP-02.2, placebo component, 28mM L-histidine and IC31® to the central Pharmacy site or the local hospital pharmacy with the relevant documentation including certificate of analysis. Further details will be provided in the pharmacy manual. Transport of lyophilised Vaccine FP-02.2, 28mM L-histidine, placebo component and IC-31® from the central pharmacy to sites will be via an approved courier and at monitored temperatures appropriate for each substance.

When the Pharmacist receives the materials for use in the study, he/she will check the conditions and contents of the package. The pharmacy staff will acknowledge receipt of the trial materials and report any anomalies in the inventory to both the Sponsor and GMP storage facility. The supplies will then be logged in to the pharmacy and the records will be updated in accordance with the pharmacy SOPs.

Lyophilised Vaccine FP-02.2 and frozen placebo component will be stored at minus 20°C (-20°C) ($\pm 5^\circ\text{C}$). Liquid IC31® adjuvant and 28mM L-histidine will be stored refrigerated, at 2-8°C. Liquid sterile NaCl 0.9% must be stored at room temperature. It is anticipated that temporary changes in temperature will occur when the refrigerator or freezer door is open for the removal of IMP as detailed in the pharmacy manual.

Records of the temperatures that Vaccine FP-02.2, IC31®, 28mM L-histidine or placebo component are stored will be maintained throughout the study. If deviations occur from the recommended storage conditions, these will be notified to the Sponsor's contact. The clinical material affected will not be used until the Sponsor has assessed the impact of the deviation and has determined whether the material can be used.

The central or hospital Pharmacy will prepare injections for all clinical sites upon receipt of a suitably signed trial-specific prescription or similar. All study drugs will be handled according to Pharmacy standard operating procedures (SOPs) and pharmacy manual. An unblinded pharmacy monitor will be permitted to check the supplies, storage and dispensing procedures. During the preparation, the Pharmacist will ensure that records are kept in sufficient detail for the sequence of operations to be determined. Sufficient reconciliation will take place in order to ensure that the correct quantity of treatment has been accounted for at each stage of the process.

Once reconstituted the IMP will be stored in the refrigerator at 2-8°C until transport to clinical sites as detailed in the pharmacy manual.

The receipt, dispensing and return of any trial material to and from pharmacy will be logged on the appropriate forms in the pharmacy.

At a time convenient to both the Sponsor and the Pharmacy all unused drugs will be returned to the Sponsor together with an account of the quantities supplied and used during the study. If required by the Sponsor, the Pharmacist will arrange for the recorded destruction of unused study drugs.

8.5 Dosage schedules

Each dose of Vaccine FP-02.2, Vaccine FP-02.2/IC31®, Placebo or IC31® will be administered as an IM injection (1.0mL) in the deltoid muscle, where possible, of the non-dominant arm by appropriately trained clinical staff members. The first dose will be administered on Day 1, the second dose approximately 4 weeks later on Day 29 and the third dose approximately 4 weeks after the second dose on Day 57. Subjects will stay in the unit for at least 4 hours following administration of the first dose and at least 2 hours following administration of the second and third doses.

8.6 Preparation and labelling of Investigational Medicinal Product

Detailed reconstitution instructions will be provided to the Pharmacies by the Sponsor. In brief:

The bulk drug product will be reconstituted at the Pharmacy as described in separate pharmacy handling instructions provided by the Sponsor. Individual subject treatments will be dispensed by the pharmacist and labelled in accordance with local Good Manufacturing Practice legislation.

Reconstitution instructions will be detailed in the Pharmacy manual.

8.7 Dosage modifications

No dosage modifications for individual subjects are allowed. The SRC may recommend reducing the dose in any treatment arm after the first dose in sentinel subjects; or the dose(s) in the next treatment arm after review of safety data at Day 36 from the previous treatment arm, as described in Section 4. In either case, the Sponsor will decide whether the study is stopped or whether to continue with a lower dose. If the dose(s) is reduced after the first dose in the sentinel subjects, those subjects will be withdrawn; if the Sponsor decides to continue, the remaining subjects in the treatment arm will be given the reduced dose(s).

8.8 Known drug reactions and interaction with other therapies

Please refer to Section 2.1.2 and the IB for an overview of the risks associated with the IMP including information about potential drug reactions. No interactions with other therapies are known so far.

8.9 Concomitant medication

In the interests of subject safety and acceptable standards of medical care the Investigator will be permitted to prescribe additional treatment(s) at his/her discretion in addition to treatment with entecavir or tenofovir.

All treatments, including vaccinations, must be recorded in the subjects' eCRFs (medication, dose, treatment duration and indication).

8.10 Trial restrictions

Women of childbearing potential must use a highly effective contraceptive method within the time frames mentioned below.

Women of childbearing potential are defined as:

- Not surgically sterile
- Not post-menopausal (post-menopausal is defined as at least one year amenorrhea in woman over 50 years. Women younger than 50 years should have laboratory confirmation of menopausal status)

Women of childbearing potential not surgically sterilised or with laboratory confirmed menopausal status are required to use a highly effective contraceptive measure with low used dependency such as:

- Combined (oestrogen and progestogen containing) hormonal contraception associated with inhibition of ovulation
- Progestogen-only hormonal contraception implants associated with inhibition of ovulation
- Intrauterine device (IUD)
- Intrauterine hormone-releasing system (IUS)
- Bilateral tubal occlusion
- Vasectomised partner – must have had medical assessment of successful surgery.

From screening until one menstrual cycle after the last dose of IMP (Day 57).

Males should fulfil one of the following criteria:

- Surgically sterile
- Willing to abstain from sexual intercourse or use a reliable form of contraception (e.g. condom), if having sex with a pregnant or non-pregnant woman of childbearing potential, from screening until 3 months after the final injection of IMP/Placebo.
- Surgically sterile female partner

8.11 Assessment of compliance

The injections will be administered by study personnel and therefore IMP compliance is not a concern. The study personnel will be appropriately trained on IMP administration procedures and documentation requirements prior to study start.

Non-compliance with study procedures will be reported to the Sponsor who will decide if persistent non-compliant subjects should be withdrawn from continued study treatment.

8.12 Name and description of each Non-Investigational Medicinal Product (NIMP)

As part of the study inclusion criteria, trial participants will currently receive either entecavir (brand name Baraclude®, Bristol-Myers Squibb) or tenofovir disoproxil furamate (brand name Viread®, Gilead) as standard of care medicine.

Additional information on these products can be found in the respective, regulated local specific documents.

Tenofovir

Tenofovir is recommended as an option for the treatment of adults with chronic HBeAg-positive or HBeAg-negative hepatitis B with compensated liver disease, with evidence of active viral replication, persistently elevated serum ALT levels and histological evidence of active inflammation and/or fibrosis. Tenofovir is a NA which works by blocking the enzyme reverse transcriptase, which is

responsible for hepatitis B virus (HBV) replication. Full details of uses, side effects and contraindications are presented in regulated local specific documents.

Entecavir

Entecavir is recommended as an option for the treatment of adults with chronic HBeAg-positive or HBeAg-negative hepatitis B with compensated liver disease, with evidence of active viral replication, persistently elevated ALT levels and histological evidence of active inflammation and/or fibrosis. Entecavir is a NA which works by inhibiting the viral DNA polymerase responsible for HBV replication, which is responsible for hepatitis B virus (HBV) replication. Full details of uses, side effects and contraindications are presented in regulated local specific documents.

9 PHARMACOVIGILANCE

9.1 Definitions

The definitions of an adverse event (AE), adverse reaction (AR), serious adverse event (SAE), serious adverse reaction (SAR), and suspected unexpected serious adverse reaction (SUSAR) are provided in Table 7 Pharmacovigilance definitions.

Table 7 Pharmacovigilance definitions

Term	Definition
Adverse Event (AE)	Any untoward medical occurrence in a participant to whom a medicinal product has been administered, including occurrences which are not necessarily caused by or related to that product.
Adverse Reaction (AR)	An untoward and unintended response in a participant to an investigational medicinal product which is related to any dose administered to that participant. The phrase "response to an investigational medicinal product" means that a causal relationship between a trial medication and an AE is at least a reasonable possibility, i.e. the relationship cannot be ruled out. All cases judged by either the reporting medically qualified professional or the Sponsor as having a reasonable suspected causal relationship to the trial medication qualify as adverse reactions.
Serious Adverse Event (SAE)	A serious adverse event is any untoward medical occurrence that: 
 • results in death • is life-threatening • requires inpatient hospitalisation or prolongation of existing hospitalisation • results in persistent or significant disability/incapacity • consists of a congenital anomaly or birth defect Other 'important medical events' may also be considered serious if they jeopardise the participant or require an intervention to prevent one of the above consequences. NOTE: The term "life-threatening" in the definition of "serious" refers to an

	event in which the participant was at risk of death at the time of the event; it does not refer to an event which hypothetically might have caused death if it were more severe.
Serious Adverse Reaction (SAR)	An adverse event that is both serious and, in the opinion of the reporting Investigator, believed with reasonable probability to be due to one of the trial treatments, based on the information provided.
Suspected Unexpected Serious Adverse Reaction (SUSAR)	A serious adverse reaction, the nature and severity of which is not consistent with the information about the IMP set out in the Investigator's Brochure (IB) relating to this trial.
Adverse Event of Special Interest (AESI)	AESI refers to adverse events of significant scientific, medical, and public interest among pandemic vaccines. For this study AESI are hepatic flares and autoimmune conditions

9.2 Operational definitions for (S)AEs

The occurrence of AEs will be assessed by non-directive questioning of the subject at each visit. Additionally, AEs volunteered by the subject during or between visits or detected through observation, physical examination, laboratory test or other assessments will be documented. Subjects will be instructed that they must immediately report any AEs, subjective complaints or objective changes in their well-being to the Investigator or the clinic personnel, regardless of the perceived relationship between event and test product.

All AEs must be fully recorded throughout the entire study period (from Screening Visit to Day 85) and will be entered into the subjects' eCRF, whether or not they are considered to be drug-related. Each AE should be described in detail: onset time and date, offset time and date, description of event, severity, relationship, action taken and outcome. From Day 85 and Day 225 only SAEs and AESIs will be collected.

Adverse events should be followed until recovery to the normal state has been achieved. In the event of a subject not returning to the clinical unit, every attempt will be made to contact the subject up to Day 85 after which the outcome of this event will be recorded as lost at follow-up.

9.2.1 Assessment of seriousness

The criteria for seriousness are provided in the definition of an SAE given in Table 7.

9.2.2 Categorisation of adverse events

The intensity of an AE will be categorised as follows:

- Mild: the event causes a minor discomfort, does not interfere with daily activity of the subject or does not lead to establishment of a correcting treatment;
- Moderate: the event perturbs the usual activity of the subject and is of a sufficient severity to make the subject uncomfortable;

- Severe: the event prevents any usual routine activity of the subject and causes severe discomfort. The term "severe" is used to describe the intensity (severity) of a specific event (as in mild, moderate, or severe myocardial infarction); the event itself, however, may be of relatively minor medical significance (such as severe headache). This is not the same as "serious," which is based on patient/event outcome or action criteria usually associated with events that pose a threat to a patient's life or functioning.

9.2.3 Assessment of causality

Causal relationship assessment to drug treatments is required for purposes of reporting AEs. To promote consistency, the following guidelines should be taken into consideration along with good clinical and scientific judgment when determining the relationship of Vaccine FP-02.2 to an AE:

- Reasonable Possibility: a causal relationship with the IMP cannot be excluded
- No Reasonable Possibility: there is no reasonable evidence to suggest a causal relationship between Vaccine FP-02.2 and the AE.
- No Possibility: there is no possibility for a causal relationship. This assessment will likely only be applied to AEs recorded prior to administration of IMP.

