10.6 Procedure(s) to account for missing or spurious data

There will be no imputation for missing data. Summaries will be over all valid cases at that time point in the applicable analysis set.

The nature and extent of missing data or spurious data will be reviewed at a blinded data review meeting.

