#### 12.6.1 Adverse Events

Adverse events will be coded using Version 20.0 or newer of MedDRA.

Treatment-emergent adverse events (TEAEs) are those which first occur or increase in severity or relationship probability to investigational product after the first dose of investigational product through 30 days after last dose of investigational product. Note that SAEs and AESIs are collected through 6 months after last dose of investigational product; therefore, all SAEs and AESIs will be summarized, not just treatment-emergent events.

All AEs which change in severity or relationship to investigational product are assigned a new start date and captured as a new record.

If more than 1 AE with the same preferred term is reported before the date of the dose of investigational product, then the AE with the greatest severity will be used as the benchmark for comparison to the AEs occurring during the study under the preferred term.

An overall summary of TEAEs, including the number and percentage of subjects who experience, and absolute count of treatment-emergent events for:

- Any TEAE
- Any TEAE by maximum severity
- Any TEAE considered possibly related to investigational product (defined as CRF response of "Reasonable Possibility")
- Any TEAE considered possibly related to investigational product by maximum severity
- Any SAEs
- Any SAEs considered possibly related to investigational product
- Any AEs with outcome of death
- Any AESIs (Hepatic flares and autoimmune conditions)
- Any TEAE leading to discontinuation of investigational product

The number and percentage of subjects reporting TEAEs, SAEs, or AESIs will be tabulated in the following ways by treatment group.

- By SOC and preferred term (including absolute count of events).
- By SOC, preferred term and maximum severity.
- By SOC and preferred term for TEAEs possibly related to investigational product in the opinion of the investigator (including absolute count of events).
- By SOC and preferred term for SAEs (including absolute count of events).
- By SOC and preferred term for possibly related SAEs (including absolute count of events).
- By SOC and preferred term for TEAEs leading to discontinuation of investigational product (including absolute count of events).
- By SOC and preferred term for AEs with fatal outcome (including absolute count of events).
- By SOC and preferred term for AESIs (including absolute count of events).

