#### **14.4 Missing Severity Assessment for Adverse Events**

If severity is missing for an AE starting prior to the date of the dose of investigational product, then a severity of "Mild" will be assigned. If the severity is missing for an AE starting on or after the date of first dose of investigational product, then a severity of "Severe" will be assigned. The imputed values for severity assessment will be used for incidence summaries, while the actual values will be used in data listings.

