#### **14.5 Missing Relationship Assessment for Adverse Events**

If relationship to product is missing for an AE, then a relationship of "Possibly related" will be assigned. The imputed values for relationship assessment will be used for incidence summaries, while the actual values will be used in data listings.

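### SAP 14.5 imputes 'Possibly related' for any adverse event with a missing relationship, including events that began before the first injection

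*Protocol*

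**What the plan says.** - **Collection.** Protocol 9.2 has all AEs recorded from the Screening Visit to Day 85, with the relationship noted for each, so pre-dose events are in the database.
- **Causality scale.** Protocol 9.2.3 has three levels: 'Reasonable Possibility', 'No Reasonable Possibility' and 'No Possibility'. Of the last it says: "This assessment will likely only be applied to AEs recorded prior to administration of IMP".
- **Missing relationship.** SAP 14.5: "If relationship to product is missing for an AE, then a relationship of" 'Possibly related' is assigned. There is no condition on onset. It adds: "The imputed values for relationship assessment will be used for incidence summaries, while the actual values will be used in data listings". SAP 12.6.1 equates possibly related with the CRF response 'Reasonable Possibility'.
- **Missing severity.** SAP 14.4 begins "If severity is missing for an AE starting prior to the date of the dose of investigational product" and assigns 'Mild' in that case. From the date of first dose onward it assigns 'Severe'.
- **Treatment-emergent events (TEAEs).** SAP 12.6.1 defines these as "those which first occur or increase in severity or relationship probability to investigational product after the first dose", up to 30 days after the last dose. For serious events and events of special interest, "all SAEs and AESIs will be summarized, not just treatment-emergent events".
- **Imputation in general.** Protocol 10.6: "There will be no imputation for missing data". Protocol 10.3 requires changes to the planned analysis to be described in the SAP. SAP 4.1 lists two changes, on physical examination and on the Immunogenicity Analysis Set.

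**The concern.** Worst-case imputation of a missing relationship is a sensible convention once product has been given. Before the first injection it assigns a causal link that cannot exist, and it puts the pre-dose event at the top of the relationship scale. Two outputs could be affected.

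First, the related-SAE counts are not limited to treatment-emergent events, so a pre-dose SAE can enter them. Second, the TEAE definition looks for a rise in relationship after dosing, and an event already at the top level cannot rise. Safety is the primary objective and the arms are small, so a single misclassified subject is visible in the tables.

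**Working it through.** The plan gives no figure to reproduce. The check traces the rules.

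**1. Related SAEs.** Take a subject with an SAE between screening and the first injection, relationship blank, who is then dosed.
- The subject is in the Safety Analysis Set (SAP 9.2: at least one injection).
- SAP 14.5 sets the relationship to 'Possibly related' for incidence summaries.
- SAP 12.6.1 summarises all SAEs, so the pre-dose onset does not remove the event.
- Result: the subject is counted in the related-SAE row of Table 14.3.2.1 and in Table 14.3.2.6. The listings still show a blank.
- Size: 1/10 = 10.0% of one arm, or 1/60 = 1.7% of the planned total. With the relationship set to 'No Possibility' the count is 0.

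A non-serious pre-dose event does not reach the related-TEAE tables by this route, because those tables require a TEAE.

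**2. TEAE flag, assuming that it uses imputed values.** Consider a pre-dose event with a blank relationship and a post-dose record under the same preferred term. The post-dose record is a TEAE if severity or relationship is higher than before. There are 3 pre-dose severities × 3 post-dose severities × 3 post-dose relationships = 27 patterns. Severity rises in 3 of the 9 severity pairs and does not rise in 6.

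- Blank set to 'Reasonable Possibility' (SAP 14.5): only a severity rise can qualify. 3 × 3 = 9 of 27 are TEAEs.
- Blank set to 'No Possibility': a pattern fails only if severity does not rise and the post-dose relationship is also 'No Possibility'. 27 − (6 × 1) = 21 of 27.
- Blank set to 'No Reasonable Possibility': 27 − (6 × 2) = 15 of 27.

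Against 'No Possibility', SAP 14.5 loses 21 − 9 = 12 patterns. In 6 of these the recurrence is judged 'Reasonable Possibility', and in the other 6 'No Reasonable Possibility'. The patterns are not equally likely, so the counts check the logic and are not rates.

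Example: mild headache at screening with a blank relationship, then mild headache on Day 2 judged 'Reasonable Possibility'. With the imputed value as benchmark, neither severity nor relationship rises, so there are 0 TEAEs and 0 related TEAEs. With 'No Possibility' as benchmark there is 1 of each.

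**3. The two adjacent rules.** SAP 14.4 sets a low pre-dose benchmark ('Mild'), so later worsening still counts. SAP 14.5 sets the highest. The two rules pull the TEAE definition in opposite directions.

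**The case against.** The strongest reply is that this will hardly ever occur. Protocol 9.2 asks for a relationship on every AE, and 9.2.3 offers a category suited to pre-dose events. SAEs are reported within 24 hours on a separate form (9.3), and the Chief Investigator or delegate assigns causality where no local assessment can be obtained (9.4). Queries are to be resolved before lock. The SAP's reason for summarising all SAEs is the six-month collection period, so capture of pre-dose SAEs looks unintended. All of this stands and limits the size of the problem. It does not make the imputed value right, and the text does not exclude pre-dose SAEs.

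Some stronger readings are tempting, but the documents do not support them:
- *That the protocol rates every pre-dose event 'No Possibility'.* The sentence in 9.2.3 is hedged and says where the category will probably be used; it does not prescribe a rating. The point rests on timing alone.
- *That 'Possibly related' lies outside the three-level scale.* SAP 12.6.1 maps it to 'Reasonable Possibility'.
- *That SAP 14.5 certainly hides TEAEs.* It confines imputed values to incidence summaries, and protocol 10.9.2 has TEAEs flagged in the listings, which keep actual values. A flag built on actual values is an equally natural reading, and then 14.5 causes no masking. Even otherwise, masking needs the same preferred term and no rise in severity.
- *That blanks are to be expected before dosing because no product had been given.* Nothing in the documents suggests this.

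**Conclusion.** The point holds as a correction to the rule. SAP 14.5 gives a causally impossible value to pre-dose events with a blank relationship and is out of step with SAP 14.4. The effect on related SAEs follows directly from the text, given a dosed subject with a pre-dose SAE and a blank relationship. The loss of TEAEs is conditional on a programming choice that the SAP leaves open; that gap needs closing in its own right.

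Each affected subject moves a 10-subject arm by 10 percentage points. The expected number is unknown and probably very small. All analyses are descriptive, listings keep actual values, and the safety review committee works from database listings (SAP 10.1), so escalation decisions are untouched. A reader might infer that the primary safety result is compromised; the documents do not support that.

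The absence of the Section 14 imputations from SAP 4.1 is a separate documentation gap, and holds however many values are missing.

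**What to change.** 1. Rewrite SAP 14.5: a missing relationship becomes 'No Possibility' for onset before the first dose and 'Reasonable Possibility' for onset on or after it. Incomplete AE start dates are already handled in SAP 14.3.1; one that matches the month and year of first dose takes the first-dose date, so it keeps the worst-case value.
2. State in SAP 12.6.1 whether the TEAE flag uses actual or imputed relationship and severity.
3. List the Section 14 imputations in SAP 4.1 as a change from protocol 10.6.
4. Optionally, footnote the number of imputed relationships in Tables 14.3.2.1, 14.3.2.5 and 14.3.2.6.

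The cost is a few sentences and one condition in the program. There is a small downside: if imputed values drive the flag, a recurrence at the same or lower severity judged 'No Reasonable Possibility' becomes a TEAE solely because the earlier blank was set to 'No Possibility' (6 of the 12 recovered patterns). That errs towards counting more TEAEs, which is the conservative direction.
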